National Taiwan University Hospital

Hsinchu Branch

Research Protocol 2018

1. Project name

Title	Prevalence and Outcomes of Peripheral Artery Disease in Sepsis Patients in the Medical Intensive Care Unit
Principal investigator	Department of Internal Medicine, Cardiovascular Division [name], Attending Physician

Table of Contents

1. Project name.....	1
2. Abstract.....	3
Background.....	3
Methods.....	3
3. Background.....	4
Prior research in this field.....	4
Sepsis and peripheral artery disease.....	4
Peripheral artery disease- its impact on the outcomes.....	4
Medications for treatment of PAD.....	4
Clinical needs.....	4
5. Goals of project.....	6
Purpose (for clinicaltrials.gov registration).....	6
Objectives.....	6
6. Methods and procedures.....	7
Research design.....	7
7. Anticipated results.....	10
8. Study progress plan.....	11
9. Assignment of Researcher.....	12
10. Funding.....	13

11. Reference.....	14
12. Appendix.....	15

2. Abstract

Background

The peripheral artery disease (PAD) has been well known for poor cardiovascular outcomes. Its prevalence is high in the elderly, in the diabetic patients, and in the patients receiving hemodialysis. To date, there is no guideline recommendation about screening of PAD in patients admitted to the medical intensive care unit (MICU) for sepsis.

Methods

We designed a prospective cohort study focusing on patients admitted to the MICU with the main diagnosis of sepsis. The ankle-brachial indexes are performed within 4 hours after admission. Invasive arterial line monitoring and standard non-invasive measurements are collected. After confirmation of PAD, standard anti-platelet treatments (aspirin and cilostazol) are initiated. The survival before and after the conduction of this trial is compared to historical records. The outcomes including all-cause mortality, stroke, myocardial infarction, minor amputation, major amputation, and prolonged ventilator dependent are to be collected.

Keywords: peripheral vascular disease, sepsis, outcomes

3. Background

Prior research in this field

Sepsis and peripheral artery disease

According to annual statistics, the sepsis cost 5.2% in 2011 medical cost in the United States. Total \$20 billions were cost for treatment of sepsis and its related medical conditions.¹ In Taiwan, the medical expenditure of patients in the medical intensive care units also is very huge. The peripheral artery disease (PAD) is also prevalent in the elderly and in most situations under-diagnosed. In Taiwan, an accurate data on PAD prevalence is absent. According to the screening program in National Taiwan University Hospital Hsinchu branch, the prevalence of PAD among patients receiving hemodialysis is high (48–30%). Many patients do not receive screening and adequate care.

Peripheral artery disease- its impact on the outcomes

Patients with PAD have four-fold increase in the risk of myocardial infarction and three-fold increase in the risk of stroke.^{2,3}

Medications for treatment of PAD

LEAD (lower extremity artery disease) is a subset of PAD. To date, there is no specific trial addressing the role of antiplatelet agents in the full spectrum of LEAD, including asymptomatic, intermittent claudication, and critical lower limb ischemia.

COMPASS ⁴	Rivaroxaban 5 mg bid Rivaroxaban 2.5 mg bid with aspirin Aspirin	Total 27402 patients with CAD or LEAD	To be reported
CAPRIE ²	Clopidogrel Aspirin		Not focused on PAD
CASPAR ⁵ CHARISMA ⁶	Clopidogrel plus aspirin Aspirin mono-therapy		Not focused on PAD
Fowkes, 2010 ⁷	Aspirin for subclinical LEAD	Asymptomatic LEAD with ABI < 0.95	No benefit
Belch, 2008 ⁸	Aspirin for subclinical diabetic LEAD	Asymptomatic LEAD in diabetic with ABI < 1.0	No benefit
Antithrombotic collaborative ⁹	Aspirin for prevention of MACE	Symptomatic LEAD	Benefit

Clinical needs

There are guidelines for treatment of sepsis and PAD. The diagnosis, treatment, and outcomes are well defined for sepsis and PAD, respectively. However, there is no consensus on the benefit of screening of PAD in patients presented with sepsis. The current diagnosis and treatment are clinically driven by patient's new change in limb physical examinations. Usually, we initiate the work-up for PAD after toe cyanosis or frank gangrene occurs.

4. Previous studies focusing on PAD in sepsis patients

There is a lack of dedicated research of PAD among patients presented with sepsis. With the search term “peripheral artery disease” and “critical care”, there is only one article on PAD and chronic obstructive pulmonary disease”.¹⁰

5. Goals of project

Purpose (for clinicaltrials.gov registration)

- Study type: interventional
- Study Design:
 - Allocation: randomized - Endpoint classification: efficacy study - Intervention model: parallel - Masking: single blind (outcomes assessor) - Primary purpose: treatment
- Official title: as the study project title

Objectives

1. Perform a screening for PAD among patients admitted to the medical intensive care units and meet the sepsis diagnosis criteria (quick SOFA score ≥ 2 points).
2. Follow the outcomes (all cause mortality at 30 days, stroke, myocardial infarction, lower limb ischemia requiring amputation) of patients who have evidence of ABI < 0.9 or PAD by additional vascular Duplex confirmation.
3. To evaluate the prevalence of PAD among patients admitted to our intensive care units.
4. To obtain the diagnosis of PAD early on the admission day among multiple care teams (cardiologists, chest physicians, and critical care specialist) and to give adequate medical treatment as needed (anti-platelet agents).
5. To evaluate whether early diagnosis of PAD in sepsis patients will lead to decision-makings that will influence the patient's survival.
6. To evaluate whether early diagnosis of PAD will lead to decreased complications rate of invasive arterial line monitoring.

6. Methods and procedures

Research design

1. Research design: prospective cohort study
2. Locations: the medical intensive care units (MICU) of National Taiwan University Hospital, Hsinchu Branch.
Patient population: sepsis patients who meet the quick SOFA score ≥ 2 points.
3. The investigator is responsible of this research: [name].
4. Study parameters:
 1. The prevalence of PAD among patients admitted to the MICU with sepsis
 2. The outcomes of PAD patients presented with sepsis to the MICU
5. Research field: critical care medicine, cardiovascular disease, peripheral artery disease
6. Keywords: peripheral artery disease, sepsis
7. Study design: observational study (cohort study)
 1. Collection of data: prospective
 2. Inter rim analysis: yes
 3. Investigator manual: yes

2. Study population

1. Patient number: 200 patients
2. Age limitation: 20-100 years old
3. Inclusion criteria:
 1. Admission diagnosis with sepsis, meeting quick SOFA criteria ≥ 2 points (respiratory rate $\geq 22/\text{min}$, altered mentation, systolic blood pressure $\leq 100 \text{ mmHg}$, each item is one point)
 2. Within the study age limitation
 3. Willing to participate the study
4. Exclusion criteria:
 1. Declined to participate
 2. Children and adolescence with age < 20 years, criminal, aboriginal, pregnant women, psychiatric patient, students, colleagues, terminal patients, soldiers,
 3. Cancer and receiving cancer treatment
5. Follow-up period: 3 months
6. Category of study: MICU study
7. Special conditions
 1. No selection by patient gender
 2. No involvement of fetal or pregnancy study of medications
 3. No involvement of healthy volunteer

4. Special protection: MICU patients have ethical committee for palliative care, every patients will have family conference by care team with the family to provide diagnosis explanation, treatment options at the bedside or the meeting room. Palliative care can be initiated anytime.
5. There is no radiation exposure in this study
8. No blood sampling
9. Enrollment procedure
 1. No additional fund will be provided to the participant
 2. The enrollment began when the patient was admitted to the MICU
10. The risk of patients is considered equal either joining in or not in the study
11. There is NO control group in this study

3. Patient information security

1. The data security team of the hospital secures the patient data. The data is located in the REDCap database and secured by the Medical Information Team of the hospital.
2. The researcher can only download de-identified data from the REDCap database (redcap.hch.gov.tw). Only the principal investigator can obtain the full dataset.
3. The following protocols are provided to protect the patient personal information:
 1. The patients can withdrawal the consent anytime. The data will be removed on patient or family's request.
There will be no compromise in the physician-patient relationship.

4. Enrollment

1. The enrollment process involves the investigator, the physicians and the nurses in the MICU.
2. Timing of enrollment: before screen process: at the entrance/meeting room of the MICU, at the time of patient admission, with oral explanation of the study intent and study method (ABI measurements), estimated time of explanation: 5 minutes
3. After the oral consent obtaining, the ABI results will be provided and explained to the family
4. Patient not speaking local language (Chinese, Taiwanese, Hakka Chinese) can still be enrolled, if physician can still communicate with English. If the communication is unsuccessful, the patient will no be enrolled.

5. Inform consent

1. This research will not require a paper inform consent. Because this study has minimal risk for the study participant- the ABI study was non-invasive. And this study will be carried in the medical intensive care units, it is focused on emergency medicine. The patients with sepsis admitted to the MICU usually are already in a critical condition and there is a need to aggressively diagnose any disease that will lead to poor outcomes. The benefits of diagnosing a PAD early outweigh the risk carried by the study method.

6. The study method

1. After enrollment, within 24 hours: the nurse will measure the ankle-brachial index (ABI). The measurements are to be done by A-line at any arteries that physician considered appropriate and additional bilateral lower limb blood pressure measurements. A Doppler scanner is allowed to be used to facilitate the measurement of ABI.
2. The definition of ABI (ankle-brachial index): the leg systolic blood pressure divided by the higher readings of bilateral brachial artery. If ABI < 0.9, a diagnosis of PAD is made.

7. The follow-up

1. At the time of admission: APACHE score
2. The treatment patient received: ventilator, vasopressor, inotropic agent, blood pressure, and the diagnosis.
3. Patient will be followed at 7 days, 30 days, and 90 days.
4. Medications will be recorded, especially: aspirin (Bokey), cilostazol (Pletal), clopidogrel (Plavix), statin.
5. Clinical events will be documented:
 1. Mortality
 2. Acute myocardial infarction
 3. Stroke, ischemic
 4. Limb gangrene resulting in amputation

8. Statistical method

1. We plan to enroll 200 patients. Patients will be grouped into patients with PAOD and patients without PAOD. We then compare them in the following parameters: clinical data, laboratory data, survival and other outcome data. Two-sample student's t tests will be used for the comparisons of continuous variables. Chi-square test will be used to detect difference between categorical variables. Difference is considered statistically significant if $P < 0.05$. All statistics works were analyzed using the SPSS 17.0 software (Chicago, IL, USA), R software (Gimc packages).

7. Anticipated results

1. Evaluate the care process and quality in patients in the MICU
2. Evaluate the prevalence of PAD in patients with sepsis admitted to the MICU
3. Investigate the influence of PAD to the outcomes of sepsis

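### No rule applies the cohort's entry exclusions, notably terminal patients, to the historical records, so the before/after survival comparison is likely, though not certain, to favour the study period

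*Combined protocol and SAP*

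**What the plan says.** The Abstract (Methods) states: "The survival before and after the conduction of this trial is compared to historical records". Item 4 of section 7, Anticipated results, asks whether mortality falls after screening, and objective 5 in section 5 also concerns survival. Section 6, Study population, says "There is NO control group in this study". The registration items in section 5 list randomised parallel allocation, but section 6 describes an observational cohort with no second arm. The Statistical method part compares only patients with and without PAOD, all of them screened, and contains no historical analysis.

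Entry to the cohort is set in section 6:

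- Inclusion: "Admission diagnosis with sepsis, meeting quick SOFA criteria" of at least 2 points, age 20-100, and "Willing to participate the study".
- Exclusion 1: "Declined to participate".
- Exclusion 2: a list containing "psychiatric patient, students, colleagues, terminal patients, soldiers", with pregnant women in the same item.
- Exclusion 3: "Cancer and receiving cancer treatment".
- Enrollment, item 4, on patients who do not speak a local language and with whom English is tried: "If the communication is unsuccessful, the patient will no be enrolled".
- Patient information security: data are removed if the patient or family asks.

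The plan does not give the dates, source or size of the historical group, does not say whether any of these criteria apply to it, and describes no case-mix adjustment. An APACHE score is collected at admission, but no analysis uses it.

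**The concern.** The mortality question rests on comparing a selected group with a group for which no selection is described. On the natural reading the study-period group is the enrolled cohort, since section 6 describes data collection for enrolled patients only. That cohort has passed a judgement about terminal status, a test of willingness and a right of withdrawal. Past patients were never asked, so the last two have no counterpart in their records. Terminal status could be approximated from charts, but the plan does not ask for that.

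The terminal exclusion matters most, because it removes patients expected to die. If it acts on one side only, the study period shows better survival whether or not screening works, and the difference would be credited to ABI measurement. Agreement on age, sepsis definition and qSOFA threshold would not cure this.

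**Working it through.** **The plan's own figure.** The only size given is 200 patients, all in the study cohort. It cannot be reproduced, because no event rate, effect size, power or historical sample size is stated. The size of the bias can therefore only be illustrated.

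**Inputs.** From the plan: 200 study patients and significance at P < 0.05 (taken as two-sided, so 2.5% in favour of the study period when nothing differs). Assumed: mortality m = 30% in patients who pass the filters; mortality q = 80% in terminal patients; terminal share f = 5%, 10% or 20% of the historical group; 400 historical patients; no effect of screening.

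**Spurious gain, terminal patients only.** Historical mortality = (1 - f) × m + f × q, so the spurious gain is f × (q - m).

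- f = 5%: 0.05 × 50 = 2.5 points (32.5% v 30%)
- f = 10%: 0.10 × 50 = 5 points (35% v 30%)
- f = 20%: 0.20 × 50 = 10 points (40% v 30%)

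**Chance of a falsely significant benefit.** For a pooled two-proportion z-test this is Φ((D - 1.96 × SE0) / SE1), where D is the spurious gain, SE0 the pooled and SE1 the unpooled standard error. For f = 10% with 200 v 400:

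- pooled mortality = (60 + 140) / 600 = 0.3333
- SE0 = √(0.2222 × 0.0075) = 0.0408
- SE1 = √(0.00105 + 0.00056875) = 0.0402
- (0.05 - 0.0800) / 0.0402 = -0.75, which gives 23%

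| Terminal share | Gain (points) | 200 v 200 | 200 v 400 | 200 v 1000 |
|---|---|---|---|---|
| 5% | 2.5 | 8% | 9% | 10% |
| 10% | 5 | 19% | 23% | 27% |
| 20% | 10 | 56% | 67% | 77% |

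**Wider range.** Over m = 20-40%, f = 5-20% and q = 60-90%, the spurious gain runs from 1 to 14 points and the false-benefit chance at 200 v 200 from about 4% to 89%. For scale, 200 v 200 has 80% power for a true reduction of about 12 points from 30%.

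**The opposite direction.** Suppose a share g of the records are low-risk patients whom the study would not enrol, with assumed mortality 10%. They cancel the terminal bias when g = f × (q - m) / (m - 10%).

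- f = 10%, q = 80%, m = 30%: 0.10 × 50 / 20 = 25%
- f = 10%, q = 80%, m = 40%: 0.10 × 40 / 30 = 13%

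With g = 5% and m = 30%, the offset is 0.05 × 20 = 1 point. That leaves 5 - 1 = 4 points at a 10% terminal share and 2.5 - 1 = 1.5 points at 5%.

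**The case against.** Four arguments can be made against the point.

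1. *The Abstract does not fix the study-period group.* Its sentence could mean survival across the whole unit in each period, and then the one-sided filter would not arise. This stands as an ambiguity. Enrolled patients are nevertheless the only ones for whom data collection is described, and the ambiguity is itself a reason to define both groups.

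2. *Terminal patients could be taken out of the records.* A reader might infer that this is impossible. The documents do not show that: section 6 describes a palliative-care ethics committee and a family conference for every MICU patient, so a chart trace is plausible. What they support is that no rule tells anyone to do it. Impossibility holds only for willingness, refusal and withdrawal.

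3. *The exclusions do not all point one way.* The item that drops terminal patients also drops students, soldiers and pregnant women, who are probably at lower risk. Records not limited to qSOFA of at least 2 would also include less ill patients. This stands, and it prevents an unconditional statement of direction. Full cancellation needs sizeable low-risk shares, which the documents neither give nor rule out.

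4. *The communication rule is not a severity filter.* A reader might take it to remove patients too ill to respond. In context it is a language rule. The documents give no mortality for language-barrier patients or for decliners, so neither group can be assigned a direction, and the illustration leaves both out.

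**Conclusion.** The point holds as a missing rule with a probable, not certain, bias. The only comparator for the mortality question sets a filtered cohort, on the natural reading, against records to which no filter is applied. The terminal exclusion alone would favour the study period by 2.5 to 10 points under the central assumptions, with a false-benefit chance of about 9% to 67% at 200 v 400. The mortalities, shares and historical sample size are all assumed, and the upper figure needs a 20% terminal share.

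A reader might conclude that the comparison must favour screening. The documents do not support that: other exclusions push the other way or have no known direction, and the make-up of both groups is unsettled. They do support the conclusion that a survival gain found in this way could not safely be attributed to ABI screening.

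**What to change.** For the before/after survival comparison only:

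- Define both periods from MICU admission records, with the same source, age range, sepsis definition and qSOFA of at least 2.
- Apply every chart-identifiable exclusion identically to both periods: cancer under treatment, one chart-based marker of terminal status at admission, pregnancy and similar items.
- Where the ethics committee allows, include non-enrolled study-period admissions through a de-identified extract. Otherwise report their number and the reasons.
- Adjust for admission severity, using APACHE where the historical records also hold it.
- Report the enrolled cohort separately, and do not attribute an unadjusted difference between it and unselected records to ABI screening.

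**Cost.** Some wording and a small record extract, with no extra patients or procedures. The downside is dilution: if a share u of study-period admissions is unscreened, a true effect d shows as (1 - u) × d. For example, with u = 20% assumed, a 10-point effect would show as 8 points.

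### As written, the ABI can divide a non-invasive leg pressure by an arterial-line pressure, so the single 0.9 cut-off need not mean the same thing in every patient

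*Combined protocol and SAP*

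**What the plan says.** The measurement is described in section 6 (Methods and procedures), under The study method. Item 1 states: "The measurements are to be done by A-line", with the choice of artery left to the physician. It adds "additional bilateral lower limb blood pressure measurements" without naming a device, and then says "A Doppler scanner is allowed to be used to facilitate the measurement of ABI", with no rule on when Doppler is to be used.

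Item 2 defines the ABI as "the leg systolic blood pressure divided by the higher readings of bilateral brachial artery", again naming no instrument, and gives the diagnostic rule: "If ABI < 0.9, a diagnosis of PAD is made".

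Two other places bear on this. The Abstract says "Invasive arterial line monitoring and standard non-invasive measurements are collected". The Inform consent section justifies waiving written consent partly because "the ABI study was non-invasive".

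The PAD diagnosis feeds the first study parameter (prevalence in MICU sepsis patients) and, reading PAOD in the Statistical method as that same diagnosis, the two groups compared on every outcome. Objective 2 also admits patients with PAD shown on Duplex, but as an alternative to a low ABI.

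**The concern.** A ratio of two pressures is robust to instrument error only to the extent that the same error affects both. If arm and leg are read by one method and the error is proportional and equal at both sites, it cancels. If one pressure comes from an arterial line and the other from a non-invasive method, any gap between the methods stays in the ratio. A fixed cut-off of 0.9 then corresponds to a different same-method cut-off, depending on which instruments were used.

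Item 1 permits this. It brings an arterial-line reading into the ABI procedure and obtains the leg pressures separately, and Doppler may be used in some patients and not in others. Naming the correct arteries would not settle it, since two correctly sited readings can still come from different instruments.

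At stake are the prevalence estimate and the makeup of the PAOD and non-PAOD groups. The Duplex route does not protect against false positives, because an ABI below 0.9 is sufficient without it. Nothing in the plan requires the method to be recorded, so the effect could not be examined afterwards.

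**Working it through.** **What the plan lets us reproduce.** N = 200 is given without an expected prevalence, precision target or power, so there is no figure to reproduce. The point concerns measurement and does not rest on how N was chosen.

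**Step 1: the passages side by side.** Item 2 needs two brachial readings and a leg reading. Item 1 supplies an arterial-line reading at a freely chosen artery plus bilateral leg pressures. One line at one site cannot give two brachial readings, so the denominator must be completed in some unstated way. No section requires one method for numerator and denominator.

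**Step 2: how an offset enters the ratio.** The pressures here are invented for illustration.
- Same method: leg 95, arm 100 mmHg gives 95/100 = 0.95 (no PAD).
- Arm alone reads 10 mmHg higher: 95/110 = 0.864 (PAD).
- Both read 10 mmHg higher: 105/110 = 0.955 (no PAD). An additive offset shared by both sites does not cancel exactly, but little of it is left here.

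**Step 3: the equivalent cut-off.** If the denominator reads b mmHg away from what the leg method would give, the nominal 0.9 acts as a same-method cut-off of 0.9 × (SBP + b)/SBP.
- SBP 100, b = −10, −5, +5, +10: 0.81, 0.855, 0.945, 0.99.
- SBP 80, same offsets: 0.787, 0.844, 0.956, 1.012.

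A fixed mmHg gap therefore distorts more as pressure falls. Systolic pressure of 100 mmHg or less is one of the three qSOFA entry items.

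**Step 4: effect on prevalence.** Assume same-method ABI is normal with mean 1.02 and SD 0.15, and the arm instrument reads r times the same-method value. Neither assumption comes from the documents. Measured prevalence is Φ((0.9r − 1.02)/0.15). If only half the patients are affected, it is the average of this value and the value at r = 1.

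| r | All affected | Shift (points) | Half affected | Shift (points) |
|---|---|---|---|---|
| 0.90 | Φ(−1.4) = 8.1% | −13.1 | 14.6% | −6.6 |
| 0.95 | Φ(−1.1) = 13.6% | −7.6 | 17.4% | −3.8 |
| 1.00 | Φ(−0.8) = 21.2% | 0 | 21.2% | 0 |
| 1.05 | Φ(−0.5) = 30.9% | +9.7 | 26.0% | +4.8 |
| 1.10 | Φ(−0.2) = 42.1% | +20.9 | 31.6% | +10.4 |

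**Step 5: sampling error.** 1.96 × √(0.212 × 0.788/200) = 0.057, or ±5.7 points. A 5% gap in all patients exceeds this in either direction. A 5% gap in half of them does not, and a 10% gap in half does.

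**Step 6: other assumptions.** With same-method prevalence of 30%, ABI SD 0.15–0.20 and SBP 100, offsets in all patients give:
- −10 mmHg: 13.0–16.5%
- −5 mmHg: 20.5–22.7%
- +5 mmHg: 38.2–41.1%
- +10 mmHg: 47.0–53.0%

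The 95% half-width at 30% is 1.96 × √(0.3 × 0.7/200), or 6.4 points.

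**The case against.** The strongest reply is that item 2 names no device, one arterial line cannot supply two brachial readings, the consent section calls the ABI non-invasive, and the Abstract lists non-invasive measurements alongside line monitoring. On that reading the ABI is wholly non-invasive and the line data are separate. This is plausible, and it rules out saying that every patient's denominator will be invasive. It does not remove the point, because item 1 says the opposite of the consent statement and is the operative instruction. An investigator manual is also listed under Research design. It is not among the documents and might fix the technique, but the protocol text does not.

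Several further limits stand:
- A reader might infer that the mixed ratio is biased. The documents give no between-method difference. If the methods agreed there would be no shift, so the most that can be said is that it can be biased.
- A reader might infer that arterial-line use varies with severity and so moves patients between groups in a way tied to outcome. The physician's discretion in item 1 covers which artery, not whether a line is used. Only Doppler is optional, and the documents do not say what would prompt its use.
- A reader might infer that ABI alone determines who is followed. Objective 2 also allows Duplex.
- The word cuff does not appear, and no leg device is named.
- A 5% gap in half the patients stays within sampling error, so the numbers do not show that instrument error must dominate.

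**Conclusion.** The point holds as one about what the plan permits. Item 1 brings an invasive pressure into a ratio whose other term may be non-invasive, lets the leg method differ between patients, applies one cut-off to all, and conflicts with the plan's own description of the ABI as non-invasive. Misclassification of PAD can follow, and it would reach both prevalence and the PAOD comparison.

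Size and direction are unknown. The illustrated shifts, roughly 8 to 21 points for a 5–10% arm offset in everyone and about 4 to 10 if half are affected, rest entirely on an assumed ABI distribution and assumed offsets. They show that modest method differences could match or exceed the sampling error of about ±6 points, not that they will. This should be changed before enrolment because it is cheap to prevent and, without a record of the method, cannot be repaired later.

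**What to change.** Rewrite item 1 of The study method so that both brachial and both ankle systolic pressures are taken by one and the same non-invasive method, using the Doppler scanner already allowed, in one sitting. Compute the study ABI in item 2 only from those readings. Record instrument and site for each reading in REDCap, and keep arterial-line pressures as separate monitoring data outside the ratio. Where a same-method reading cannot be obtained, flag it and report prevalence by method. Reconcile the A-line wording with the statement in the consent section that the ABI is non-invasive.

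The cost is a protocol wording change, a few REDCap fields and a few minutes of nurse time per patient.

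### The ABI rule has no upper limit and PAOD is undefined, so a falsely high or unobtainable ABI falls into the comparator unless Duplex happens to be done

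*Combined protocol and SAP*

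**What the plan says.** The operational rule is in Section 6, The study method, item 2. It gives the ABI and its only cut-off as "the leg systolic blood pressure divided by the higher readings of bilateral brachial artery. If ABI < 0.9, a diagnosis of PAD is made". Nothing states an upper limit, an indeterminate category, or what to do when an ankle pressure cannot be obtained.

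Item 1 of the same part describes the measurement. It provides for an arterial line at a site the physician chooses, plus "additional bilateral lower limb blood pressure measurements. A Doppler scanner is allowed to be used to facilitate the measurement of ABI". It does not say whether leg pressures are taken by cuff.

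The statistical method (Section 6, part 8) says: "Patients will be grouped into patients with PAOD and patients without PAOD". PAOD is not defined there or elsewhere.

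Objective 2 (Section 5) describes the followed group differently, as "patients who have evidence of ABI < 0.9 or PAD by additional vascular Duplex confirmation". Duplex does not appear in the study method or the statistical method.

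On PAD, the Abstract states: "Its prevalence is high in the elderly, in the diabetic patients, and in the patients receiving hemodialysis". The exclusion criteria name neither diabetes nor dialysis, and the upper age limit is 100.

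**The concern.** A cuff cannot properly compress a stiff ankle artery, so the ankle pressure, and with it the ABI, can read high in a leg with poor flow. This is general vascular knowledge and is not stated in the documents. Such a reading is uninformative rather than negative. Under the study-method rule it is nevertheless not PAD, and in a two-group analysis the patient joins the comparator.

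Both listed study parameters, the prevalence of PAD and the outcomes of patients with PAD, rest on this one classification. True cases counted as unaffected lower the prevalence. If PAD carries a worse prognosis, they also raise the comparator's event rate and narrow the difference. Enrolling more patients does not remove this bias.

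**Working it through.** The plan gives no expected prevalence, event rates, precision target or power for its 200 patients, so there is no figure of its own to reproduce. The steps below are an illustration.

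**Inputs**
- From the plan: N = 200 and the single cut-off of 0.9.
- Assumed: 60 patients have an ABI below 0.9. The resulting 30% equals the lower of the two haemodialysis screening figures in Section 3; the plan has no figure for sepsis.
- Assumed: 5–10% of patients (10 to 20) have a high ABI, and 50–80% of those truly have PAD.
- Assumed: mortality is 45% with PAD and 25% without, Duplex recovers none of the missed cases, and there is no other ABI error.

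**Step 1, missed cases.** 10 × 0.5 = 5, up to 20 × 0.8 = 16.

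**Step 2, prevalence.**
- Reported: 60/200 = 30.0%.
- True: (60 + 5)/200 = 32.5%, up to (60 + 16)/200 = 38.0%.
- The shift is 2.5 to 8.0 points. The 95% half-width at 30% is 1.96 × √(0.3 × 0.7/200) = 6.4 points, so only the upper part of the range exceeds sampling error.

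**Step 3, comparator.** It holds 200 − 60 = 140 patients. The misclassified share is 5/140 = 3.6%, up to 16/140 = 11.4%.

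**Step 4, mortality contrast.** Observed difference = 20 × (1 − misclassified share).
- 20 × (1 − 5/140) = 19.3 points.
- 20 × (1 − 16/140) = 17.7 points.

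**Step 5, if missed cases do worse.** Take 60 true cases, 12 of them missed, with an assumed 60% mortality in the missed.
- True PAD mortality is 0.8 × 45 + 0.2 × 60 = 48%, so the true difference is 48 − 25 = 23.0 points.
- Comparator mortality is (140 × 0.25 + 12 × 0.60)/152 = 27.8%, so the observed difference is 17.2 points.

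**Step 6, would a separate category help?** Prevalence under each handling:

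| High-ABI patients | Counted non-PAD | Excluded | Counted as PAD | Assumed truth |
|---|---|---|---|---|
| 10 | 60/200 = 30.0% | 60/190 = 31.6% | 70/200 = 35.0% | 32.5–34.0% |
| 20 | 60/200 = 30.0% | 60/180 = 33.3% | 80/200 = 40.0% | 35.0–38.0% |

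Exclusion and counting as PAD bracket the assumed truth in both rows. The current rule lies below it.

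For the contrast, no single handling is always right. Under the Step 4 assumptions, exclusion restores 45 − 25 = 20 points. Under Step 5 it gives 20 points against a true 23.0. All three handlings should therefore be shown.

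**The case against.** Four points on the other side have weight.

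- **Duplex.** A reader might infer that the rule is strictly binary and that every high ABI must end up in the comparator. The documents do not support that, because Objective 2 admits PAD shown by Duplex and the statistical method does not say that grouping uses the ABI alone. What remains is that nothing sends a high ABI to Duplex or says whether Duplex can override it.
- **Arterial line.** A pressure read directly from an ankle artery would not depend on compressibility. The plan does not require this, so the error is possible but conditional on cuff measurement.
- **Direction and frequency.** A reader might infer that the reported prevalence will certainly be too low. That is not established. The documents do not say how often high readings occur. Patients with systolic pressure of 100 mmHg or less can qualify, and falsely low ABI values in hypotension could offset the error.
- **Risk label.** A reader might take the plan to call elderly, diabetic and dialysis patients high-risk for this error. It says only that PAD is common in them, and it plans no analysis within those groups.

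The objection that the effect is small also stands in part: most of the illustrated range is within sampling error for prevalence, and the loss in the contrast is modest.

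**Conclusion.** The gap is real and inexpensive to close. The study method, Objective 2 and the statistical method do not agree on what places a patient in the PAD group, and a high or unobtainable ABI defaults to the comparator. Where leg pressures are taken by cuff, this particular error biases prevalence downward and, if PAD worsens outcome, biases the contrast toward the null. The illustrated size is 2.5 to 8.0 points of prevalence and 0.7 to 2.3 points of an assumed 20-point mortality difference, or more if missed cases fare worse than detected ones. Every input except the sample size and the cut-off is assumed. The actual size, and the net direction over all ABI errors, cannot be settled from the documents.

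**What to change.** 1. In the statistical method, define PAOD and reconcile it with the study method and Objective 2, so that a Duplex result, where one exists, has a stated role in group membership.
2. In The study method, item 2, prespecify an upper ABI limit, with its value justified by the sponsor, and cover the case where ankle pressure cannot be occluded. Class such patients as 'ABI non-diagnostic' if they have no leg below 0.9 and no Duplex-confirmed PAD.
3. Report the number and outcomes of these patients as a third category. Give prevalence and the outcome contrast three ways: with them excluded, counted as PAD, and counted as non-PAD.

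Fix the limit before outcomes are examined. The change takes a few sentences and uses ABI values already collected. Under the illustration, the main comparator falls from 140 to between 130 and 120 patients, with slightly lower precision. This is an analysis category only and changes no treatment.
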